6.1. Study Subjects

6.1.1. Disposition of Subjects

Patients may exit from the study at any time and for any reason. Stop of data collection for patients in the study may occur due to the following reasons:

- Withdrawal of consent
- Patient lost-to-follow-up
- Patient death
- Patient did not undergo the instrumented lumbar fusion as defined in CIP

Patients who terminate from the study will be summarized by the reasons for termination according to the categories in the CRF at each visit. An accountability table will also be provided to summarize the disposition of patients, including number of patients discontinued from the study, number of patients having follow-up, and follow-up.

6.1.2. Clinical Investigation Plan (CIP) Deviations

In this study, potential CIP deviations are defined as deviations related to:

- Data release or patient informed consent procedure
- Enrolled patient does not meet inclusion/exclusion criteria
- Visit not done
- Assessment(s) at the visit not performed
- Visit outside the CIP defined visit window
- Patient did not undergo the instrumented lumbar fusion as defined in CIP
- Improper Serious Adverse Event (SAE)/Adverse Device Effect (ADE)/Serious Adverse Device Effect (SADE) reporting (please see section Table 5 AEs of this CIP)
 - Any (U)(S) A(D)Es, device deficiencies with SADE potential and serious procedure related AEs, that are not reported timely
 - Any AE or device deficiency without (S)A(D)E potential that is not reported within 20 calendar days
- Ethical Committee (EC)/Institutional Review Board (IRB) approval not obtained, if required

Details of CIP deviations will be summarized descriptively. Subjects with deviations will be summarized by type of deviations listed above and by follow-up visit.

6.1.3. Analysis Datasets

The primary analysis dataset defined in this study comprises of all subjects who are enrolled and receive a single or double level instrumented fusion using MAST™ minimally invasive PLIF, TLIF, DLIF, OLIF, ALIF and MIDLIF surgical procedures with a mandatory posterior fixation. For double levels instrumented fusion, the same procedure must be used for both levels. All the analyses will be carried out on the

This document is electronically controlled. Printed copies are considered uncontrolled.

Confidential

primary analysis dataset. For subjects who are enrolled but not included in the primary analysis dataset, their demographic and other baseline characteristics will be summarized separately. The reasons for not using minimally invasive procedure or surgery not done will be listed as well.

In addition to the primary analysis dataset, four subgroups are defined in the following:

- 1) DDD patients with spondylolisthesis and stenosis
- 2) DDD patients with spondylolisthesis but without stenosis
- 3) DDD patients with stenosis but without spondylolisthesis
- 4) All patients not included in subgroups 1), 2), 3).

The analysis for the primary endpoint and secondary endpoints outlined in secondary objectives 2 and 3 (section 4.2) will be performed on these four subgroups as well. For the primary analysis dataset and each of these four subgroups, the analysis will be carried out on further subgrouped by anterolateral and posterior groups.

Other subgroup analysis such as by number of treated levels may also be performed.

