## **E.3 Baseline procedures**

During the baseline visit the following data will be collected, patient demographics, medical history, comorbidities, surgery indication, pain medication, work status, imaging data. A standardized visual analogue scale (VAS, 0-10) will be used to evaluate the level of leg and back pain as perceived by the patient prior to surgery. Quality of life will be assessed having the patient completing the EQ-5D. Evaluation of how back or leg pain is affecting the patient's ability to manage in everyday life will be assessed using the Oswestry Disability Questionnaire (ODI). Neurological status; in case of a neurological abnormality, the neurological status will be assessed and documented. The measurement of Slip and Disk Height of the levels adjacent to the index level(s) will be collected by X-Ray, CT scan and/or MRI whichever is applicable at the site. The identification of neuropathic pain will be assessed by the DN4 questionnaire in the back and in the leg.

Sagittal Balance will be collected in those sites where it is standard of care by collecting an X-Ray (preferably this would be a long standing / full spine X-Ray (C7 + Femoral Head visible) or alternatively a short X-Ray with the femoral heads and top of lordotic segment visible).

AEs should be collected after patient signed consent/data release form.

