## **E.4 Implant or procedure aspects**

Patients will receive a single or double level instrumented fusion using a minimally invasive/MAST™ **PLIF, TLIF, DLIF, OLIF, ALIF or MIDLF** surgical procedure with a posterior fixation. The use of a posterior fixation system is mandatory in this study and will be either mini-open and/or percutaneous.

Only those investigators with a documented experience of at least 30 minimal invasive procedures are allowed to perform the procedure of the subjects in this study.

It is recognized that the situation of a patient might change after enrollment. Due to investigator's discretion a patient who was scheduled for a minimally invasive lumbar fusion procedure might receive an open procedure, might not be operated to treat the degenerative lumbar spine or might have a different procedure for other reasons.

It is at the investigator discretion to decide before or during the surgery that the patient does no longer meet the eligibility criteria of the study to perform a Minimally Invasive Fusion Surgery. If this situation occurs this shall be documented on a study deviation eCRF (please see section E.11) and appropriate action should be taken (see section E.10) as well as a rationale for either continuing with the minimally invasive procedure, continuing with an open procedure or for discontinuation of the procedure and the study early termination form will be completed in the eCRF.

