## E.9 Adverse events

All AEs, regardless of relatedness to surgical procedure or outcome, should be reported throughout the study in the CRF and should be made available to the Medtronic study team. If applicable, these events will be reported to other countries where studies are conducted with the same or a similar product. All AEs will be screened immediately for possible product complaints, to allow compliance with the 48-hours reporting requirement.

In China, the Clinical safety reporting requirements are governed by the following China Food and Drug Administration (CFDA) documents.

- CFDA Notice No. 766: Measure on Medical Device Adverse Events Monitoring and Reevaluation
- CFDA Guidance document No. 425: Device Adverse Event Monitoring (Interim)

CFDA Notice No. 766 and CFDA Guidance document No. 425 are vigilance reporting requirements in China.

Since there is no country specific clinical safety reporting requirement for this study in China, the common safety reporting process for all participating regions/countries will be followed in China.

In Korea, The clinical safety and vigilance reporting requirements are governed by the following MFDS's (The Ministry of Food and Drug Safety) documents.

- MFDS Notification 2014-178 (Revised on Oct 31, 2014): Regulations for Approval of Clinical Trial Plan.
- Ministerial Decree No.1307 (Effective on Jul 29, 2016): Enforcement Regulations of the Medical Device Act including KGCP
- MFDS Notification No.2016-2 (Revised on Jan 14, 2016: Regulations on - Management of Medical Device Safety Information, Including Adverse Event Report.

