## **G DATA ANALYSIS AND REPORTING**

### **G.1 Analysis of clinical data**

For the purpose of the analysis, all subjects who are enrolled and undergo a minimally invasive lumbar fusion procedure will be included in the analyses. All the analyses will be based on observed data. No missing data will be imputed.

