6.10. Safety Evaluation

The analyses include:

- Time-to-event (life table method) to assess the cumulative AE rate up to 4-week, 1-year, 2-year, 3-year, 4-year and 5-year visit intervals.
- Summary of number of AEs and number of subjects having AEs up to the 5-year visit.
 - All AEs
 - Serious Adverse Events (SAE)
 - Device related AEs
 - MAST™ Approach/Procedure related AEs
 - General Surgery related or Lumbar Fusion procedure related AEs
 - Disease related AEs.
 - Serious device related AEs
 - Serious MAST™ Approach/Procedure related AEs

A relatedness determination of "possible", "probable" or "causal relationship" is considered "related".

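### The SAP plans no adverse-event output for enrolled patients outside the primary analysis dataset and leaves converted cases unclassified

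*SAP*

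**What the plan says.** **Who is analysed.** SAP 6.1.3 defines the primary analysis dataset as enrolled patients who received a one- or two-level minimally invasive fusion by one of the six procedures, with mandatory posterior fixation and the same procedure at both levels if two were treated. It then applies all analyses to that set. Protocol G.1 is broader: "all subjects who are enrolled and undergo a minimally invasive lumbar fusion procedure will be included in the analyses". It mentions neither posterior fixation nor the same-procedure rule.

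**What the others get.** "For subjects who are enrolled but not included in the primary analysis dataset, their demographic and other baseline characteristics will be summarized separately" and "The reasons for not using minimally invasive procedure or surgery not done will be listed as well". They can also appear in the disposition table (SAP 6.1.1) and the deviation summary (SAP 6.1.2), since both carry a category for patients who did not have the defined fusion.

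**How such patients arise.** Enrollment is at consent (protocol E.2). Under E.4 a patient scheduled for minimally invasive fusion "might receive an open procedure, might not be operated to treat the degenerative lumbar spine or might have a different procedure for other reasons". The investigator may also "decide before or during the surgery that the patient does no longer meet the eligibility criteria of the study", and then go on minimally invasively, go on open, or discontinue the procedure.

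**What AE data exist.** "AEs should be collected after patient signed consent/data release form" (E.3) and "All AEs, regardless of relatedness to surgical procedure or outcome, should be reported throughout the study in the CRF" (E.9). Protocol B.1.3 names AEs as a secondary endpoint and says all of them will be analysed.

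**Planned AE outputs.** SAP 6.10 begins with "Time-to-event (life table method) to assess the cumulative AE rate up to 4-week, 1-year" and later intervals to 5 years. It adds counts by seriousness and relatedness, and names no population of its own.

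**The concern.** The plan collects AEs in a group of enrolled patients and then gives those events no place in any AE output. Patients never operated, or switched to open surgery beforehand, say little about the safety of the study procedures. For them the issue is mainly complete reporting of what was collected.

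Cases converted or abandoned during surgery matter more, because membership of the dataset then depends on what happened in the operation. Protocol E.9.1.1 assigns events from the access, decompression and instrumentation steps, including dural tears and nerve root injury, to the category for the MAST approach or procedure. If an access-stage event is followed by conversion, and the case is then classed as outside the dataset, the event is missing from the summary meant to count it.

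**Working it through.** **Step 1: follow the AE of a patient outside the dataset through the SAP.**

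| SAP section | Includes patients outside the dataset? | AE output for them? |
|---|---|---|
| 6.1.1 Disposition | Yes, by reason for termination | No |
| 6.1.2 Deviations | Yes, by deviation type | No (only late or improper AE reporting counts as a deviation) |
| 6.1.3 Datasets | Yes, baseline summary and list of reasons | No |
| 6.8 Interim analyses | No separate population named | No |
| 6.10 Safety | No separate population named, so 6.1.3 applies | No |

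No row yields an AE table, listing or rate for them.

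**Step 2: settle who is inside and outside.**

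- Inside: a patient who had the defined fusion and later left the study. SAP 6.4 analyses data up to exit.
- Inside: a patient switched from one of the six procedures to another, if the definition is still met.
- Outside: not operated, plainly treated open, or fusion abandoned.
- Outside under SAP 6.1.3 but inside under protocol G.1: a minimally invasive fusion without posterior fixation, or with different procedures at two levels.
- Not stated: begun minimally invasively and finished open. Protocol K.5 defines open and minimally invasive procedures but not a converted case.

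**Step 3: scale.** The documents give no figure to reproduce and no conversion, abandonment or not-operated rate. What can be computed is the most that one omitted patient can move a proportion k/n:

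- Patient with the event: (k+1)/(n+1) − k/n = (n−k)/(n(n+1)), at most 1/(n+1), when k = 0.
- Patient without the event: k/n − k/(n+1) = k/(n(n+1)), at most 1/(n+1), when k = n. This fall exceeds the rise above when k > n/2.

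| n analysed | Source | Largest shift per patient |
|---|---|---|
| 350 | anticipated enrollment | 1/351 = 0.28 points |
| 280 | required total | 1/281 = 0.36 points |
| 175 | 350/2, even split assumed | 1/176 = 0.57 points |
| 140 | 280/2, even split assumed | 1/141 = 0.71 points |

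**Step 4: could the gap be empty?** As pure illustration, assume 1%, 3%, 5% or 10% of 350 fall outside: 4, 11, 18 or 35 patients, rounded up. If each has probability p of at least one AE between consent and exit, the chance that at least one patient's AE goes untabulated is 1 − (1−p)^m.

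| p (assumed) | m = 4 | m = 11 | m = 18 | m = 35 |
|---|---|---|---|---|
| 5% | 19% | 43% | 60% | 83% |
| 10% | 34% | 69% | 85% | 97% |
| 20% | 59% | 91% | 98% | nearly 100% |

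Over most of this assumed range the gap is more likely than not to contain something, but the table is not evidence about this trial.

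**The case against.** **The population is a legitimate choice.** The aim is to describe the safety of minimally invasive fusion, so patients never exposed to it do not belong in its rates. This stands, and it is why the fix gives those patients a separate listing or table rather than a place in the denominators.

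**The restriction of 6.10 is inferred.** That section names no population, 6.1.1 and 6.1.2 already reach beyond the dataset, and B.1.3 promises analysis of all AEs. This stands in part. Still, 6.1.3 is the only population rule the safety section can inherit, and the all-AEs line in 6.10 heads a list of event types rather than defining patients. If wider coverage was intended, the SAP should say so.

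**Other channels exist.** Individual review and reporting by the sponsor continue (E.9.1.2, E.9.1.4), and a complication that forced conversion could surface in the reasons listing. Both are true, but neither is an AE count or listing in the study report.

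**A stronger reading.** A reader might infer that the plan will understate approach-related harm. The documents do not support that as a general statement. For converted cases it depends on an unstated classification. How often conversion or abandonment occurs, and whether it differs by approach, is unknown. E.4 ties the decision to eligibility and unspecified other reasons, not to complications.

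**A stronger remedy.** One might move all 6.10 outputs to everyone in whom surgery was started. That could mislead: E.10 lets data collection stop for patients without the defined fusion, so adding them to counts running to 5 years could dilute late-event proportions, and their early exit could make censoring in the life tables informative.

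**Conclusion.** The gap is real on the text. Followed as written, the SAP leaves AEs collected from enrolled patients outside the primary analysis dataset out of every planned AE output, contrary to the intention in protocol B.1.3. That includes access-stage events in abandoned cases. For converted cases the loss is conditional on their being classed as outside.

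The correction is minor. The 6.10 analyses are descriptive, and no hypothesis test is touched. Each omitted patient moves an overall proportion by at most 0.28 to 0.36 points, or 0.57 to 0.71 points within an approach group if the groups are equal in size, up or down. The total effect cannot be stated because the number of such patients is unknown.

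**What to change.** In SAP 6.1.3 and 6.10:

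1. State that cases in which a minimally invasive study procedure was started and then converted or abandoned enter a supplementary peri-operative AE summary by relatedness, up to the 4-week interval already used in 6.10. Group them by attempted approach where existing CRF, deviation or surgery data identify it.
2. Keep the 5-year counts and life tables on the primary analysis dataset.
3. Add an AE listing or table, from consent to study exit, for all other enrolled patients outside that dataset.
4. Reconcile the 6.1.3 population with protocol G.1, so that it is clear where a minimally invasive fusion without posterior fixation, or with different procedures at two levels, is counted.

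**Cost.** SAP wording, one flag and one or two extra outputs. The AEs themselves are already collected. Whether attempted approach can be derived without a new field cannot be confirmed, because the CRF is not part of the documents. Peri-operative AE rates may shift slightly in either direction. Because E.10 limits follow-up of these patients, the gain is mainly for events before, during and soon after surgery.

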6.2. General Methodology

In this study, the two-sided 95% CI will be conducted to test hypothesis for primary and the first secondary objectives. For other analyses without hypothesis testing, the analyses are descriptive in nature. In general, the categorical variables will be summarized using frequency tables and continuous variables will be summarized using mean, standard deviation, median, minimum and maximum.

Time-to-event (life table method) will be performed to estimate the cumulative event rate up to 5 years for secondary surgery at index levels or adjacent levels and AEs.

Time-to-event analysis will be conducted for fusion success.

6.3. Center Pooling

This study will be conducted in approximately 30 sites located in Europe, Latin America and Asia Pacific. A test of analysis of covariance (ANCOVA) will be performed to check whether data are poolable across different regions for the primary endpoint. The ANCOVA model includes the change of ODI at 3 months as dependent variable, and region, procedure group (anterolateral versus posterior) and interaction between region and procedure group as factors, and baseline ODI as covariate. We anticipate Latin America has less subjects treated than other regions. If Latin America has less than 10 subjects in each procedure group, subjects in this region will be combined with subjects in Europe. If the region factor is not statistically significant, the pooling data across regions is justified and pooling data from all regions is planned for final statistical analyses. Otherwise, the results from each region will be presented separately.

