#### **G.1.1 Analysis of Primary Endpoint**

To evaluate whether the primary endpoint improvement in ODI at 3 months is equivalent for the spondylolisthesis DDD subjects treated with anterolateral approaches and the ones treated with posterior approaches, the two-sided 95% confidence interval for the mean difference of ODI improvement at 3 months will be calculated. If the 95% CI is within the equivalent range of (-10, 10), then the primary objective is met. In addition, the paired t-test will be carried out for each group to see whether the ODI improvement at 3 months from baseline is significant.

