#### **G.1.4 Interim Analysis**

In addition to a final statistical analysis, an interim analysis will be conducted when all subjects reached 3-month visit. At that time, the 3-month data including the primary endpoint improvement of ODI at 3-month visit from baseline will be finalized and the conclusion for the primary endpoint will remain unchanged at the final analysis.

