4.2. Secondary Objectives and Endpoints

The secondary objectives include:

1. To evaluate whether DDD patients without spondylolisthesis fare equally well regardless of the surgical procedure (anterolateral or posterior) performed, as measured by endpoint which is defined as improvement of ODI at 3 months as compared to baseline.
2. To observe and document clinical and radiological outcomes through 5-year follow-up (except for ODI at 3 months). Endpoints include improvement of ODI as compared to baseline, improvement of VAS back- and leg pain intensity as compared to baseline, improvement of EQ-5D as compared to baseline, neurological success, fusion success, secondary surgeries at index and /or adjacent level(s) and adverse events (AE).
3. To observe and document the patients' short term recovery after surgery. Endpoints include time needed for first ambulation and surgery recovery day.
4. To document health resources consumption and perform economic analyses.
5. To observe and document the patient profile when choosing a particular minimally invasive fusion procedure.

5. Determination of Sample Size

Taking into account the literature information and the opinion of the Study Advisory Board, the "equally well" is defined as the mean difference in ODI improvement at 3 months between the anterolateral and posterior group is within the equivalence range of (-10, 10) points, which indicates if the mean difference between the anterolateral procedures group and the posterior procedures group is within the range of (-10, 10) points for the ODI improvement at 3 months, the anterolateral and posterior treatment options will be considered equivalent in terms of effectiveness.

Assuming that the standard deviation for ODI improvement at 3 months is 20 for both groups (anterolateral and posterior) and there is no difference in the mean ODI improvement at 3 months, with 80% power and 5% alpha level, the sample size per group is 70 and 140 in total in order to claim equivalence of the primary endpoint between two groups with equivalent margin (-10, 10).

From the MASTERS-D study it is known that approximately 50% of the patients with degenerative disc disease have spondylolisthesis \geq grade I. Hence the required total sample size is $140/0.5 = 280$.

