6.9.1. Primary Objective

The study hypothesis for the primary objective is to verify whether DDD patients operated for spondylolisthesis (\geq grade I) have equivalent mean improvement of ODI at 3 months regardless of anterolateral or posterior procedure used.

The hypothesis includes:

$$H_0: \Delta_{ODI_anterolateral} \neq \Delta_{ODI_posterior}$$

$$H_a: \Delta_{ODI_anterolateral} = \Delta_{ODI_posterior}$$

This document is electronically controlled. Printed copies are considered uncontrolled.

Confidential

Where $\Delta_{ODI_anterolateral}$ is the average improvement in ODI score (baseline – 3 months) in spondylolisthesis subjects treated with the anterolateral approach and $\Delta_{ODI_posterior}$ is the average improvement in ODI score (baseline – 3 months) in spondylolisthesis subjects treated with the posterior approach.

ANCOVA will be performed with baseline ODI as covariate and the two-sided 95% CI for the least square mean difference of ODI improvement between two groups at 3 months will be calculated. If the 95% CI is within the equivalent range of (-10, 10), then the primary objective is met. In addition, the paired t-test will be carried out for each group to see whether the ODI improvement at 3 months from baseline is significant.

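### SAP 6.3 decides regional pooling on the region factor, attaches no consequence to the region-by-approach interaction, and does not say whether the pooled 6.9.1 criterion still decides when region is significant

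*SAP*

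**What the plan says.** SAP 6.3 (Center Pooling) fits an ANCOVA of the 3-month ODI change on region, approach (anterolateral or posterior), the "interaction between region and procedure group as factors", and baseline ODI. The decision sentence is "If the region factor is not statistically significant, the pooling data across regions is justified". The alternative is "Otherwise, the results from each region will be presented separately". No significance level is given, and no sentence uses the interaction result. A small-region rule applies to one region: "If Latin America has less than 10 subjects in each procedure group", it is merged with Europe.

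SAP 6.9.1 sets the success criterion without reference to region or to 6.3: "If the 95% CI is within the equivalent range of (-10, 10), then the primary objective is met". Its model names baseline ODI as the only covariate. Protocol G.1.1 uses the same margin and says that "the two-sided 95% confidence interval for the mean difference of ODI improvement at 3 months will be calculated"; it has no regional pooling rule. Protocol G.1.4 fixes the result at the 3-month analysis, after which "the conclusion for the primary endpoint will remain unchanged at the final analysis". SAP 6.3 speaks of pooling for the final analyses, while SAP 6.8 sends the interim analysis to the methods in 6.2 and does not mention 6.3.

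**The concern.** The primary quantity is a difference between approaches. A regional shift in mean improvement that both approaches share leaves that difference unchanged, provided the approach mix is balanced across regions. The term that shows whether the difference varies by region is the interaction. On its plain wording, 6.3 acts on the first term and leaves the second without consequence. It can therefore separate the regions over a shift common to both approaches, and pool them over a strong interaction.

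The text also leaves open what happens to the primary objective once region is significant. Regional results may be shown beside the 6.9.1 result or in place of it. With no statement either way, the choice could be made after the data are seen, and G.1.4 then locks it in.

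A related problem is confounding. Protocol B.6 rules out randomization, and B.7 states that the mix of procedures is not the same in all regions. A regional shift can then bias the approach contrast, and the 6.9.1 model has no region term. A non-significant region test does not exclude this.

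**Working it through.** **Inputs from the documents.** Margin ±10; true difference 0; 70 per group; "the standard deviation for ODI improvement at 3 months is 20 for both groups" (SAP section 5); two-sided 95% CI (SAP 6.9.1); about 50% of patients with spondylolisthesis (SAP section 5); Latin America with 3 estimated sites and a maximum of 20 patients per site (enrollment-limits table, Protocol B.7; limits may change).

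**Assumed, not in the documents.** Two regions of 90 and 50 among the 140 patients; approaches balanced within region (45/45 and 25/25) unless stated; pooling test at 0.05; the shifts, interactions and mixes below. Baseline ODI is not simulated. Percentages in steps 3 and 4 come from 20,000 simulated trials per scenario.

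**1. The plan's own figure.** For equivalence at true difference 0, n = 2 × [SD × (z(1−α) + z(0.90)) / margin]². With one-sided α = 0.05: 2 × [20 × (1.645 + 1.282)/10]² = 68.5, so 69; the t-based calculation gives 70 with 80.6% power. The stated 70 is reproduced. That corresponds to a 90% CI. With the 95% CI in 6.9.1, 70 per group gives about 67%, which is the baseline used below. This mismatch is a separate matter.

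**2. Regional CI half-width**, t × SD × √(2/n):
- n = 70 per group: 1.977 × 20 × √(2/70) = 6.7.
- n = 32: 9.99. Below this, at SD 20, the interval cannot be expected to fit within ±10.
- n = 15 (Latin America: 3 × 20 = 60; × 0.5 = 30; evenly split, 15): 2.048 × 20 × √(2/15) = 15.0. The chance of meeting ±10 is 0.03%.
- n = 10 (a size that 6.3 keeps separate): 18.8.

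SD 20 is the SD of improvement, and baseline adjustment could lower it. At an assumed residual SD of 17, n = 15 gives 12.7 and a chance of 0.5%.

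**3. Shift common to both approaches, no approach difference.** The SE of the regional contrast is 20 × √(1/90 + 1/50) = 3.53. For a 5-point shift the region test is significant with probability about Φ(5/3.53 − 1.98) = 29%.

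| Shift | Region significant | Pools and meets ±10 | Meets ±10 if 6.9.1 stands |
|---|---|---|---|
| 5 | 29% | 47% | 66% |
| 8 | 61% | 26% | 66% |
| 10 | 80% | 13% | 64% |

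The third column matters only if regional results replace 6.9.1.

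**4. Opposite effects, −15 (region of 90) and +15 (region of 50), equal regional means.** The interaction SE is 20 × √(2/45 + 2/25) = 7.06, and 30/7.06 = 4.25, so the interaction is significant in 99% of trials. The region test is significant in 5%, so the rule pools in 95%. The average difference is (−15 × 90 + 15 × 50)/140 = −4.3, which lies inside ±10.

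**5. Unequal mix.** Bias of a model without region = shift × (difference between approach groups in the proportion coming from the shifted region).
- Anterolateral share 36% vs 76% (cells 32/58 and 38/12): (38 − 12)/70 = 0.371, so 1.9 points at a shift of 5 and 3.0 at a shift of 8.
- Share 46% vs 58% (cells 41/49 and 29/21): (29 − 21)/70 = 0.114, so 0.6 and 0.9 points.
- SE without region: 20 × √(2/70) = 3.4. With region in the strong-mix case: 20/√(32×58/90 + 38×12/50) = 20/√29.74 = 3.7.

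**The case against.** **Regional results may simply be additional.** This is the better-supported reading. SAP 6.9.1 and Protocol G.1.1 state the criterion without condition, SAP section 3 takes the protocol as its guide, and SAP 6.12 records no change to the planned analysis. On this reading the power loss in step 3 does not occur. It is not conclusive: 6.3 offers separate presentation as the alternative to pooling, and 6.12 is weak evidence because the ANCOVA in 6.9.1 is itself not in G.1.1.

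**Pooling over an interaction is not an error for the stated hypothesis.** Protocol B.4 and SAP 6.9.1 compare average improvement between approach groups, and no passage claims equivalence within each region. This stands. A reader might infer from step 4 that the rule yields false claims of equivalence; the documents do not support that, because the average of −4.3 is truly inside the margin.

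**The region factor could be read to include the interaction**, since the model sentence lists it among the factors. That is possible, but 6.3 does not say so, and the plain meaning is the main effect.

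**The region main effect is not irrelevant here.** Correct: with unequal mix it can confound, so a common shift is harmless only under balance. The regional and per-procedure limits in Protocol B.5, B.7 and E.1 may even out the mix but do not guarantee it.

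**The population of the test is open.** SAP 6.1.3 runs all analyses on all treated patients, and 6.3 does not restrict its test to spondylolisthesis. With 350 patients (225/125) a 5-point shift would be significant in about 61%: the SE is 20 × √(1/225 + 1/125) = 2.23. This adds to the need for clarification.

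**Conclusion.** The point holds as a mis-specified decision rule with an unstated consequence, and it should be fixed. On its plain wording 6.3 decides on a term that does not show whether the approach difference varies by region, gives the term that does no role, and leaves unsaid which result decides the primary objective when region is significant.

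The size depends on the reading. If regional results replace 6.9.1, common shifts of 5 to 10 points take the chance of pooling and meeting equivalence from 64–66% down to 47–13%, and a region with 15 per group has almost no chance of meeting ±10 alone. If they are additional, that loss is nil. It would be too strong to say that the plan loses this power. Under either reading the interaction changes nothing in the decision, and the harm is a conclusion stated without the qualification that it is an average over regions. Confounding by region is a possible bias of about 0.6 to 3.0 points under the assumed mixes and shifts. Regional sizes, shifts, mixes and the 0.05 test level are assumptions; the gap in the text does not depend on them.

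**What to change.** 1. State in SAP 6.3 and 6.9.1 that the pooled approach difference in spondylolisthesis patients is the primary result whatever the region test shows, including at the 3-month analysis where the conclusion is fixed.
2. Replace the region-factor rule with a report, in the same population, of the region-by-approach interaction (estimate and 95% CI) and of the approach difference in each region with its 95% CI, as supportive results. State that the primary conclusion is an average over regions and that a non-significant interaction does not show consistency: at effects of −5 and +5, p < 0.10 is reached in only about 41% of trials (10/7.06 = 1.42 against a critical value of 1.66). For the same reason, do not make the claim depend on an interaction p-value.
3. Prespecify the 6.9.1 ANCOVA with region as an added factor, as a sensitivity analysis.

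The cost is a few lines of SAP text and one extra model, with no new data. The region-adjusted interval is wider if the mix is strongly unbalanced (SE about 3.7 against 3.4), but as a sensitivity analysis it leaves the primary power unchanged.
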